An assessment of acute toxicity (clinician- and patient-reported skin, breast and oesophageal symptoms measured using CTCAE v5.0 and PRO-CTCAE v5.0) will be performed with the aim of identifying any early safety signal with either of the test schedules. The primary endpoint for this analysis, on which the sample size is based, is clinician-reported CTCAE v5.0 skin toxicity. Grade ≥ 3 acute skin reactions are expected to be low, about 3% in the control group. The aim of this analysis will be to rule out $\geq 10\%$ acute skin reactions CTCAE v5.0 grade ≥ 3 in either test group. Based on an A'Hern single-stage design with 90% power and 5% one-sided significance level, this would require 103 participants in each of the test groups. The same number of patients will be included from the control group to confirm the design assumptions, but this will be a non-comparative analysis. Allowing for approximately 10% of patients missing the relevant assessment data (or excluded from the per protocol population on which this analysis will be based), approximately 345 patients will be included in this sub-study. If 6/103 or more participants within either test group have CTCAE v5.0 skin reactions \geq grade 3 then it would not be possible to exclude a 10% rate.

Sample size for subgroup analysis of pneumonitis rates in IMC population.

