Acute lung toxicity is a specific consideration relevant to patients receiving radiotherapy to the IMC (expected to be 10-15% of recruited patients). As such, a powered subgroup analysis to evaluate this is planned. Based on RTOG assessment, the rate of $\geq G3$ pneumonitis occurring up to 3 months post-treatment in patients requiring radiotherapy to the IMC is anticipated to be 2% in the control group and we want to rule out an increase of 3% (to 5%) or more in the test groups. The two test groups will be combined for this analysis since the mean dose to the lung for both schedules is almost identical. Using an A'Hern single stage design with 90% power and a 5% one-sided significance level, 311 participants receiving IMC radiotherapy in either of the experimental arms would allow a rate $> 5\%$ to be ruled out. Rates of pneumonitis in control arm patients requiring IMC radiotherapy will be considered for the purpose of confirming the design assumptions but this will be a non-comparative analysis. If more than 9/311 cases of $\geq G3$ pneumonitis were reported in those receiving 5Fr SIB, then it would not be possible to exclude a rate of 5% or more.

Sample size for late normal tissue effects analysis.

Late normal tissue effects, and particularly breast induration, are important secondary endpoints of the trial. An analysis of clinician-assessed breast induration at 3 years is planned with the aim of demonstrating that there is not an unacceptable increase in risk of these symptoms associated with either of the test schedules. Based on IMPORT HIGH(6), we expect 11% of patients to have moderate/mark clinician-assessed breast induration by 3 years in the control group. A sample size of 823 patients per arm will provide 90% power to rule out an increase of 5% (to 16%) or more in either of the test groups (2.5% alpha for each pairwise comparison). This analysis will be based on the per protocol population. Allowing for approximately 20% of patients missing the relevant assessment data (or excluded from the per protocol population), the anticipated timing of this analysis is when 3090 patients have reached 3 years follow-up after randomisation.

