10.5. Interim Analyses and Stopping Rules

An Independent Data Monitoring Committee (IDMC) will be formed and will confidentially review accumulating safety and efficacy data from the trial at regular intervals (at least annually). Given the non-inferiority hypothesis, and that primary endpoint events will accrue slowly relative to recruitment timescales, early stopping on the basis of efficacy is not expected to be relevant and so no formal interim analysis or

stopping rules are in place. However, at each review, the IDMC will consider the balance of risks and benefits in the accumulating data, as well as any emerging external evidence, in making recommendations to the TSC regarding continuation of the trial.

At the time of analysis for the Early Side-Effects Sub-Study, if 6 or more participants (out of 103) within either test group have skin reactions \geq grade 3 (on CTCAE v5.0) then it would not be possible to exclude a 10% rate and this will provide stopping guidelines on which the IDMC will base their recommendations. PRO-CTCAE v5.0 data will also be considered. Similarly, for the subgroup analysis of IMC patients, 9 or more cases of RTOG \geq grade 3 pneumonitis in the first 311 IMC patients receiving 5Fr SIB (either test group) would mean a 5% rate could not be excluded and provides stopping guidelines on which the IDMC will base their recommendations. In both cases, consideration will also be given to the observed control arm rates for these toxicities and whether these align with design assumptions. Unless the IDMC advise otherwise, recruitment will continue whilst these analyses are undertaken.

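### Sections 10.1 and 10.5 give opposite answers at exactly 9 of 311 pneumonitis cases, and only the 10.1 boundary has the stated 5% error and 90% power

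*Protocol*

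**What the plan says.** Protocol section 10.1, on the sample size for pneumonitis in the IMC population, says the rate "is anticipated to be 2% in the control group and we want to rule out an increase of 3% (to 5%) or more" on the 1-week schedules. The design is stated as follows: "Using an A'Hern single stage design with 90% power and a 5% one-sided significance level, 311 participants receiving IMC radiotherapy" from the two experimental arms. On pooling, it says "The two test groups will be combined for this analysis". The boundary then follows: "If more than 9/311 cases of" grade 3 or worse pneumonitis occur on the 5-fraction schedules, a rate of 5% or more cannot be excluded. Under this wording, 9 cases still excludes 5%.

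Protocol section 10.5 restates the boundary as the guideline for the IDMC: "for the subgroup analysis of IMC patients, 9 or more cases of RTOG" grade 3 or worse "pneumonitis in the first 311 IMC patients receiving 5Fr SIB (either test group) would mean a 5% rate could not be excluded". Under this wording, 9 cases does not exclude 5%.

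The endpoint, the patients, the denominator and the target rate are the same in both sections.

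**The concern.** One outcome, 9 cases in 311, is classified in opposite ways by two current sections, and nothing else in the Protocol settles which applies. Each sentence states when a 5% rate can be excluded, so they cannot be read as two rules for two purposes.

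Section 10.5 names this count as the reference for the IDMC's recommendation. Section 10.4 also plans to publish the analysis before the primary endpoint, as reassurance about the 5-fraction approach. With 9 cases, the Protocol would support both the claim that 5% is excluded and the claim that it is not. Choosing between them at that point would be a decision made after seeing the data. A further question is whether the 10.5 boundary has the operating characteristics stated in 10.1.

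**Working it through.** **Inputs, all from section 10.1 except the second boundary**
- Expected rate p1 = 2%; rate to be excluded p0 = 5%.
- One-sided significance level 5%; power 90%.
- n = 311, both test groups combined.
- Boundary A (10.1): fails with 10 or more cases, passes with at most 9.
- Boundary B (10.5): fails with 9 or more cases, passes with at most 8.

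**Formula.** For a single-stage exact design that passes with at most k cases:

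P(X ≤ k | n, p) = Σ (x = 0 to k) C(n, x) p^x (1 − p)^(n − x)

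The error is this probability at p = 5% (wrongly excluding a true 5%). The power is this probability at p = 2%.

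**Step 1: reproduce the stated design.** The smallest n for which some k gives error ≤ 5% and power ≥ 90% is n = 311, with k = 9. The neighbouring sizes show how tightly 311 is tied to k = 9:

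| n | error, k = 9 | power, k = 9 |
|---|---|---|
| 310 | 0.0509 (too high) | 0.9038 |
| 311 | 0.0497 | 0.9022 |
| 312 | 0.0484 | 0.9007 |
| 313 | 0.0472 | 0.8992 (too low) |

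The sample size in 10.1 is therefore correct and belongs to the boundary given there.

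**Step 2: compare boundaries at n = 311.**

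| Passes with at most | error at 5% | power at 2% | fails at a true 2% |
|---|---|---|---|
| 8 (section 10.5) | 0.0252 | 0.8257 | 1 − 0.8257 = 17.4% |
| 9 (section 10.1) | 0.0497 | 0.9022 | 1 − 0.9022 = 9.8% |
| 10 | 0.0885 | 0.9494 | 1 − 0.9494 = 5.1% |

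Only k = 9 meets both stated error rates. Under 10.5 the power is 90.2 − 82.6 = 7.6 percentage points lower, and a true 2% rate meets the guideline 17.4 / 9.8 = 1.78 times as often.

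**Step 3: test the 10.5 statement on its own terms.** With 9 cases in 311, the exact one-sided p-value against 5% is P(X ≤ 9 | 311, 0.05) = 0.0497, and the one-sided 95% upper limit is 4.996%. At the Protocol's own level, 5% is excluded. With 10 cases the upper limit is 5.39% and 5% is not excluded.

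**Step 4: how often the sections disagree.** They differ only at exactly 9 cases:
- at a true 2%: 0.9022 − 0.8257 = 0.0765, or 7.7%;
- at a true 5%: 0.0497 − 0.0252 = 0.0245, or 2.4% from the unrounded values.

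**Step 5: the parallel skin rule.** Section 10.1 has "If 6/103 or more participants within either test group have CTCAE v5.0 skin reactions" of grade 3 or worse, and section 10.5 uses the same count of 6 or more in 103. Passing with at most 5 of 103 gives error 0.0479 at 10% and power 0.9099 at 3%, as designed. The mismatch is confined to pneumonitis.

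**The case against.** Several points can fairly be made in the plan's defence.

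- **The sample size is right.** Section 10.5 states no error rate or power. Within 10.1 the size, error, power and boundary all agree. This stands: the fault is an inconsistency between sections, probably a slip in transcription, and the 82.6% is what follows if 10.5 is applied as written.
- **The boundary is advisory.** Section 10.5 says there are no formal stopping rules, has the IDMC weigh the observed control-arm rates, and lets recruitment continue unless the IDMC advises otherwise. This also stands. The higher failure rate at 2% means more frequent crossing of a guideline, which is not the same as more frequent stopping.
- **The 10.5 version is the cautious one.** Its chance of wrongly excluding a true 5% rate is 2.5% instead of 5.0%. The cost is false alarms, and no harm is more likely to be missed.
- **The reach is small.** This is one non-comparative subgroup safety analysis. The disagreement concerns a single count, and the primary endpoint and total sample size are untouched.

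These points limit the consequence but do not remove the contradiction. An advisory guideline still needs one reference number, and both sentences are worded as statements of statistical fact. Nor can the matter be left to the statistical analysis plan, because the Protocol has already fixed the boundary twice, in conflict.

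**Conclusion.** The concern holds. Sections 10.1 and 10.5 contradict each other at exactly 9 of 311 cases, and only the 10.1 boundary delivers the stated design (error 4.97%, power 90.2%). The 10.5 boundary has error 2.5% and power 82.6%, and it raises the chance of meeting the guideline at the expected 2% rate from 9.8% to 17.4%. Its statement that 9 cases leaves 5% unexcluded is not true at the one-sided 5% level.

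The figures assume independent patients with a common event rate, exactly 311 evaluable patients, and the exact binomial test that an A'Hern design implies. Although the discrepancy is one event and lies in the cautious direction, it should be corrected before the analysis because it sits in the threshold named as the basis for the IDMC's recommendation.

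**What to change.** Reconcile sections 10.1 and 10.5 so that one boundary appears in both. Two courses are consistent with the arithmetic:

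1. Word 10.5 as more than 9 (that is, 10 or more) cases in 311. This matches the sample size, error and power already stated in 10.1.
2. Keep 9 or more in 10.5, change the boundary in 10.1 to match, and restate the operating characteristics there as about 83% power and 2.5% one-sided error with n = 311.

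Which guideline to adopt is for the sponsor and the IDMC. The choice should be recorded before the pneumonitis data are reviewed. The cost is a few words in the Protocol, plus the same correction in the IDMC charter if it repeats the boundary. No change to the number of patients or to data collection is needed.

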Risks and benefits of 1-week radiotherapy for people with breast cancer who require treatment to the internal mammary chain (IMC): Patients requiring radiotherapy to nodes behind the breastbone (IMC) were not included in the FAST-Forward Nodal Sub-Study since data demonstrating a survival gain of IMC radiotherapy were only published more recently and therefore SOC for this patient group will remain as 3-week radiotherapy even beyond the FAST-Forward Nodal Sub-Study primary analysis(28). The population of patients eligible for FAST-Forward Boost (generally younger women and those with higher grade cancer more likely to have lymph node involvement) will be enriched for patients requiring IMC radiotherapy. This group is currently anticipated to make up 10-15% of the eligible population, with this proportion anticipated to increase following Lancet publication of a meta-analysis supporting the use of IMC radiotherapy in several patient subgroups with lymph node involvement(8). Whilst relative effects on local recurrence would be expected to be comparable to those seen in FAST-Forward and FAST-Forward Nodal Sub-Study, it remains necessary to demonstrate that 1-week IMC radiotherapy is not associated with any increase in lung toxicity (pneumonitis) within the first 3 months from treatment. This is especially pertinent in the modern era of breast cancer management where many patients are receiving increasing adjuvant systemic treatment (e.g. TDM-1, immunotherapy) of which pneumonitis is a recognised side effect. These treatments were not routinely given in the FAST- Forward/IMPORT HIGH recruitment period. FAST-Forward Boost will provide these data and can be extrapolated to those without boost since associated lung doses would be no higher.

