The trial will also incorporate a recruitment sub-study to assess barriers and facilitators to recruitment in under-served populations (UK only) and two embedded “Studies Within A Trial” (SWATs) considering a new tool for assessing skin toxicity across a range of skin tones, and patient/ healthcare professional views on carbon trade-off decisions in clinical trials. These will be added/activated at a later date.

The trial is 8.5 years in duration including 3.5 years accrual period and 5 years of trial follow-up. Additional follow-up beyond 5 years via routinely collected healthcare datasets (or alternative methods, including ongoing routine data collection at site, where this is not possible) will inform later analyses of long-term outcomes.

This trial has been co-designed with patients and public involvement. Focus groups were held after a national advert (to FAST-Forward trial centres, NIHR People in Research, NIHR BRC Cancer Patient Voice Platform, Independence Cancer Patient Voice, ICR social medial channels and networks linked to co-applicants including Black Women Rising) seeking input from those with lived experience of breast cancer. Over 40 people took part. Patient and Public Involvement (PPI) contributors have been clear that shorter radiotherapy treatment is desirable if it does not compromise the risk of cancer returning. They prioritised local recurrence as the primary endpoint (rather than breast hardness as originally planned) and requested detailed data collection (quantitative & qualitative) about early and late side-effects of SIB, specifically fatigue & QoL, and data that

has not been captured in previous radiotherapy studies (impact on employment/caring, support needed by friends/family during radiotherapy and recovery). The PPI Lead and an additional member will form part of the TMG. Four PPI members reviewed the patient information sheets and informed consent forms.

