5. PATIENT SELECTION & ELIGIBILITY

5.1. Number of Participants

The aim is to recruit 4830 participants, 1610 into each group of the study.

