10.2. Treatment Allocation

All trial participants will receive radiotherapy.

Participants will be allocated between the three groups – control, test group 1 and test group 2 - on a 1:1:1 basis (open-label). Allocation will be by computer generated random permuted blocks. Randomisation will be stratified by:

- breast surgery type (breast conservation surgery (including mammoplasty) or breast conservation surgery with perforator flap reconstruction)
- need for nodal radiotherapy (none, nodes not including IMC or nodes including IMC)
- treating centre.

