10.4. Statistical Analysis Plan

Statistical analyses will be conducted at the ICR-CTSU. Analysis details are outlined here in brief. Full details will be specified in a Statistical Analysis Plan in accordance with ICR-CTSU Standard Operating Procedures. Health economics analysis will be conducted by the University of York and detailed in a separate analysis plan (Appendix A3 provides further details of the health economic evaluation).

Timing of the analyses

Subject to guidance from the IDMC, the primary analysis is expected to take place when all patients have completed a minimum of 4 years follow-up in the trial (or are known to have been lost to follow-up or withdrawn), with a median follow-up time of approximately 5 years. A later analysis, incorporating routinely collected healthcare data (subject to validation), will focus on long-term cancer outcomes.

Some secondary endpoint data will mature whilst the trial is ongoing and it is intended that results from these analyses will be published ahead of primary endpoint data, to provide reassurance of the safety of the 5Fr approach. These include:

- Early side effects sub-study analysis, including acute toxicity and dosimetry data (103 patients in each test group with relevant CTCAE v5.0 data)
- Subgroup analysis of pneumonitis rates in IMC population (including at least 311 patients receiving IMC radiotherapy in either test group with relevant 3-month RTOG data)
- Late normal tissue effects analysis (including 823 patients in each trial arm with the relevant 3-year data on breast induration)

Analysis sets

Primary efficacy analyses will be based on the intention-to-treat analysis set (including all patients according to allocated trial arm). However, given the non-inferiority hypothesis, sensitivity analysis based on a per protocol analysis set will also be conducted to consider the impact of non-compliance and draw robust conclusions about non-inferiority. Safety analyses will be based on a per protocol analysis set, according to treatment received. Full definitions of the analysis sets will be provided in the analysis plan.

Analysis of the primary endpoint

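### The only pre-specified pneumonitis guideline is tied to 311 assessed IMC test-group patients, a set complete at about month 30 to 44 of a 42-month accrual, with no missing-data allowance, so it comes too late to serve fully as an interim safeguard

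*Protocol*

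**What the plan says.** Section 10.1 of the protocol plans a single-arm test of grade 3 or worse RTOG pneumonitis in patients having IMC radiotherapy, pooling the two test groups. It takes 2% as the anticipated rate and 5% as the rate to rule out, with one-sided 5% significance and 90% power, and arrives at 311 patients. IMC patients are "expected to be 10-15% of recruited patients".

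Section 10.4 sets when the analysis is done: "including at least 311 patients receiving IMC radiotherapy in either test group with relevant 3-month RTOG data". Section 10.5 turns it into a stopping guideline for the IDMC: reaching the stated number of cases "in the first 311 IMC patients receiving 5Fr SIB (either test group) would mean a 5% rate could not be excluded". It adds: "Unless the IDMC advise otherwise, recruitment will continue whilst these analyses are undertaken".

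The quantities that fix the timing are in section 5.1 ("The aim is to recruit 4830 participants, 1610 into each group of the study"), section 3 ("The trial is 8.5 years in duration including 3.5 years accrual period and 5 years of trial follow-up") and section 8.6, which places the lung assessment 3 months after the start of radiotherapy. Section 1.1 also gives 10-15% as the current expectation for the IMC share, "with this proportion anticipated to increase following Lancet publication of a meta-analysis supporting the use of IMC radiotherapy", but attaches no figure to the increase.

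Section 10.5 also has the IDMC review accumulating safety data at least once a year and weigh risks and benefits each time.

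**The concern.** A stopping guideline is useful as an interim safeguard only if it can speak while there are still patients to protect. This one is a fixed count attached to a fixed denominator in a small subgroup. Once the failing number of cases has occurred, no later patient can reverse the result, yet the text links the guideline to the completed set of 311.

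The other reporting routes do not fully cover the gap. Section 1.1 says pneumonitis peaks around 3 months after radiotherapy. SAE reporting (sections 9.1 and 9.3) ends 30 days after the last fraction. AE reporting to 7 weeks (section 9.2) covers the early side-effects sub-study only. Pneumonitis is also on the list of expected toxicities (section 9.4), so it would not ordinarily qualify for expedited reporting. The 3-month RTOG assessment is therefore the main systematic source.

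A second issue is feasibility. The skin calculation allows about 10% for missing or excluded patients and the induration calculation about 20%. The pneumonitis calculation states no allowance, so the planned number and power may not be delivered at the low end of the protocol's own IMC share.

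**Working it through.** **The plan's own figure.** With X binomial, find the smallest n and cut-off c such that P(X ≤ c | 5%) ≤ 0.05 and P(X ≤ c | 2%) ≥ 0.90. The exact search gives n = 311 and c = 9, with P(X ≤ 9 | 5%) = 0.0497 and P(X ≤ 9 | 2%) = 0.902. The 311 is reproduced.

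**The two stated limits.** Section 10.1 fails the test groups at more than 9 cases, and section 10.5 at 9 or more. If 9 cases already fail, the figures become P(X ≤ 8 | 5%) = 0.025 and P(X ≤ 8 | 2%) = 0.826. The passages need reconciling. The calculations below use 10 cases as the failing count, as in section 10.1.

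**When 311 are assessed.** Inputs: 4830 recruits allocated 1:1:1 (sections 5.1 and 10.2), so 4830 × 2/3 = 3220 in the test groups; accrual of 3.5 years = 42 months; lung assessment at 3 months. Even accrual is assumed, because the protocol gives no accrual curve. Month = 42 × 311 / (3220 × share) + 3.

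| IMC share | IMC test patients in whole trial | 311th recruited | 311th assessed |
|---|---|---|---|
| 10% | 322 | month 40.6 | month 43.6 |
| 12.5% | 402.5 | month 32.5 | month 35.5 |
| 15% | 483 | month 27.0 | month 30.0 |
| 20% (illustrative) | 644 | month 20.3 | month 23.3 |

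By month 30, 4830 × 30/42 = 3450 participants (71%) are randomised; by month 44 all are. A slower start, illustrated as 350 recruits by month 9 and an even rate after that, moves the 10-15% range to about month 32 to 44.

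**Missing data.** At a 10% share the margin is 322 − 311 = 11 patients, and 11/322 = 3.4%. Above that, 311 is never reached. With an assumed 10% missing, 322 × 0.9 = 290 remain. The boundary is then at most 8 cases: P(X ≤ 8 | 5%) = 0.044 and P(X ≤ 8 | 2%) = 0.869. At a 15% share with 10% missing, 311 / 0.9 = 346 patients are needed and the set is complete at about month 33.

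**When the failing count would occur.** The expected number of patients to the 10th case is 10 / rate. At a true 10% rate that is 100 patients, or about month 12 (15% share) to 16 (10% share), including the 3-month lag. At a true 5% rate it is 200 patients, or about month 20 to 29.

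**What a month-24 IDMC review could see.** Patients assessed = 3220 × share × (24 − 3)/42, which is 161 at a 10% share and 241 at 15%.

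| True rate | P(10 or more cases), 10% share | P(10 or more cases), 15% share |
|---|---|---|
| 2% | 0.002 | 0.024 |
| 5% | 0.29 | 0.77 |
| 10% | 0.97 | above 0.99 |

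**The case against.** A reader might infer that the guideline cannot protect participants at all. The documents do not support that. Section 10.5 has the IDMC look at accumulating safety data at least annually without waiting for 311 patients, and section 11.3 lets it release side-effect data at any stage. A gross excess would very probably have produced the failing count by month 24.

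The text can also be read more generously. The wording about the time of analysis is attached to the skin rule. The pneumonitis sentence states a count within the first 311, which an IDMC could act on as soon as it saw it. What is tabulated at each review may be settled in the IDMC charter or the statistical analysis plan, neither of which is shown. The IMC share is expected to rise, which brings the date forward. At a 12.5% share, up to 22.7% could be missing (1 − 311/402.5) before 311 became unattainable. Because the analysis waits for 311 with data, missing data usually delays it without reducing power. The 3-month assessment may be remote, so losses may be lower than for in-person skin visits. Finally, the analysis is also meant to support publication ahead of the primary endpoint, and its timing serves that purpose.

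Most of this stands, and it limits the point. It does not remove it. The annual reviews carry no pneumonitis threshold before 311, so acting on the count would be discretionary. At 5%, the rate the design exists to exclude, the count may well not have been reached by month 24. Curtailment also gains less at 5% than at 10%. A reader might further infer that the skin guideline has the same weakness, but no timing problem is shown there and no change to it is proposed.

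**Conclusion.** The point holds as one of late and fragile timing. On the stated 10-15% share, the set that carries the only pre-specified pneumonitis guideline is complete at about month 30 to 44 of a 42-month accrual. At the 10% end, more than 3.4% missing means it is never complete. The guideline therefore applies too late to serve fully as an interim safeguard, although the regular IDMC reviews give partial protection. If only 290 were evaluable, power would fall from the stated 90% to 87%, a modest loss.

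These results rest on even accrual, a constant IMC share and, except where stated, no missing data. A slower start makes the dates later. A share above 15%, which section 1.1 makes possible, makes them earlier. The 10% missing figure is an assumption, since the protocol gives none for this analysis.

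**What to change.** First reconcile the case limit between sections 10.1 and 10.5. Then:

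- **Section 10.5:** state that the reconciled boundary applies by curtailment, so that the IDMC is notified as soon as the failing number of cases is reached, whatever the denominator at that moment. State also that the running count of grade 3 or worse pneumonitis in IMC test-group patients, with the number assessed, is tabulated at each scheduled IDMC review.
- **Section 10.1:** state a missing-data allowance for this analysis, and the boundary and power if fewer than 311 are evaluable. For example, 290 evaluable gives at most 8 cases, one-sided significance level 0.044 and power 87%.

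The cost is wording in the protocol and IDMC charter, plus a little extra tracking. A failing count reached before 311 is also a failing count at 311, so the final decision and its error rates do not change.
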